7.4 Electronic Case Report Forms

The study eCRFs are the primary data collection instrument for the study. All data requested on the eCRF must be documented. All missing data must be explained. It is expected that eCRFs be completed and that any forms requiring signature are electronically signed by the investigator within 2 weeks of the evaluation date.

7.5 Data Queries

If errors or omissions are noted by Stryker upon review of the data entered into the eCRFs, a query will be sent to the center within the EDC system. Queries should be answered in a clear and comprehensible manner.

7.6 Protocol Deviations

Any major deviation from this protocol will be recorded by the Sponsor and must be reported to the EC/IRB by the investigational site according to their reporting procedures. Major protocol deviations for this study may include the following; this list may not be all-inclusive:

- Informed consent deviations, including but not limited to:
 - Study procedures performed prior to informed consent
 - Incorrect informed consent version used
- Patient enrolled does not meet the inclusion/exclusion criteria
- Protocol specified study component(s) not implanted
- Visit deviations, including:
 - Unavailable primary endpoint

If the center anticipates a possible protocol deviation, the investigator or SC should contact Stryker for guidance.

7.7 Records Retention

It is the investigator's responsibility to retain study essential documents for 2 years after the date of the final report, or 2 years after the date of investigative center termination. These documents should be retained for a longer period if required by an agreement with Stryker.

8 Statistical Plan

8.1 Study Objectives

8.1.1 Primary Objective Analysis

The primary hypothesis to be tested will be that the mean SF-36 Physical Score (PCS) at 2-years postoperative with a cemented Triathlon Total Knee with the Triathlon PSR Insert is not worse than 47.3 with a non-inferiority margin of 2.5 points. That is, the following hypothesis will be tested:

H0:
$$\mu \le 47.3 - 2.5$$
 vs HA: $\mu > 47.3 - 2.5$

Here, μ is the mean SF36 PCS at 2-years postoperative with a cemented Triathlon Total Knee with the Triathlon PSR insert. The reference value of 47.3 was derived from Triathlon PS study where subjects received a cemented Triathlon PS Total Knee with the PS Insert. (NCT00957021).

A 90% two-sided confidence interval (CI) will be computed for the mean SF36 PCS at 2-years postoperative. If the lower bound of the CI is greater than 44.8, then the non-inferiority holds. If the lower bound of the CI is greater than 47.3, then the mean SF36 PCS at 2-years postoperative is superior to 47.3.

8.1.2 Secondary Objective Analyses

The Kaplan-Meier survival curve of all-cause revision and removal of the Triathlon PSR insert will be displayed using SAS/PROC LIFETEST at 10-years postoperative. The survival rate at 10 years will be presented with a 95% CI.

The ROM at 2 years will be compared with 124 degrees, as derived from Triathlon PS study, using an equivalence margin of 5 degrees. A TOST (two one-sided test) will be used with SAS/PROC TTEST to test the difference.

The change between the preoperative and postoperative EQ-5D TTO scores will be tested with Paired T-tests.

The analysis for the additional data collected is in **Section 8.4.1**.

8.2 Safety

8.2.1 Safety Parameters

Safety parameters include all protocol-defined adverse events as well as all-cause revision and/or removal of any component of the Triathlon Total Knee with the Triathlon PSR Insert. For details regarding protocol-defined adverse events, see **Section 6.1**.

8.2.2 Safety Analyses

The frequency and percentage of all protocol-defined adverse events will be tabulated. All protocol-defined adverse events will be tabulated, and a 95% CI will be presented. For details regarding protocol-defined adverse events, see **Section 6.1**.

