6.1 Reporting of Adverse Events

The AE reporting requirements for this study are as follows:

[figure not shown]
- All AEs that meet the definition of serious (see page 22) and occur within the perioperative period (intraoperative to hospital discharge) to 90 days postoperative
- All AEs related to the operative site, regardless of seriousness or time of occurrence

On postoperative functional evaluations, investigators and SCs will be prompted to question subjects as to whether they have seen a doctor for any reason, been hospitalized for any reason or have a current impediment to their function.

For the 6-, 7-, 8-, 9-year intervals, only a Follow-up Questionnaire will be administered. SCs will be responsible for following up with the subjects regarding any questionable responses received on the Follow-up Questionnaire. If it is determined upon this further investigation that a protocoldefined AE has occurred, the SC will be responsible for completing an AE eCRF, submitting the event to Stryker, and reporting the event to the IRB as required.

The following decision tree facilitates identification of AEs for which reporting is required under this study protocol:

Figure 1. Adverse Event Decision Tree

General Physical Examination Findings

At screening for inclusion into the study, any clinically significant abnormality should be recorded as a preexisting condition and reported on the Demographics eCRF. From the time of consent forward, any new clinically significant findings or abnormalities that meet the definition of a protocol defined AE must also be recorded and documented as an AE.

Adverse Event Reporting Period

The study period during which AEs must be reported is normally defined as the period from the initiation of any study procedures to the end of the study treatment follow-up. The start of study procedures is considered to be the point of consent. Any AEs which fit the protocol defined reportable events must be reported from the time of consent until study completion.

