At each contact with the subject the investigator must seek information on AEs by specific questioning and, as appropriate, by examination. Information on protocol defined AEs should be recorded immediately in the source document and also in the appropriate AE module of the eCRF. All clearly related signs, symptoms and abnormal diagnostic procedure results should be recorded in the source document and grouped under one diagnosis, as appropriate. The clinical course of each event should be followed until resolution or until it is determined at the end of the study that the AE will not resolve.

All operative site events occurring at any time as well as all serious adverse events (SAEs) occurring within the perioperative period to 90 days postoperative will be collected and compared to published data. It is expected that the AE rates reported for the Triathlon Total Knee with the Triathlon PSR insert will be comparable to those for historical Triathlon PS cemented constructs.

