8.4.2 Sample Size Justification

Based on the Triathlon PS clinical study, it is reasonable to have a SF36 PCS reference value of 47.3 (with a standard deviation of 10.7) at 2-years postoperative. Two hundred cases are needed to have a power of 95% to detect that the mean SF36 PCS at 2-years postoperative is non-inferior to the reference value with a margin of 2.5 at 5% significance level. After factoring in a 20% lost to follow-up rate, a total of 250 cases will be needed.

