11.3 Expected Complications

Complications associated with TKA procedures, such as those performed with the study device, have been reported. These include the potential for but are not limited to: infection, genitourinary disorders, gastrointestinal disorders, vascular disorders, bronchopulmonary disorder, myocardial infarction, injury to the knee's neurovascular structures, loosening of the components, osteolysis, heterotopic bone formation, deep vein thrombosis, pulmonary embolism, metal sensitivity reactions, intraoperative or postoperative fracture of the femur, patella or tibia, and the need for re-operation, revision, arthrodesis of the involved joint, amputation of the limb and death. The safety analysis will include tabulation of AE rates as well as revision/removal rates.

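### Operative-site AEs over 10 years, and revisions that leave the PSR insert in place, are summarised only as crude percentages, with no allowance for unequal follow-up

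*Combined protocol and SAP*

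**What the plan says.** - **Collection window.** The synopsis follows each case to 10 years. Section 6.1 requires reporting of "All AEs related to the operative site, regardless of seriousness or time of occurrence". Other serious AEs are reportable only up to 90 days after surgery.
- **Safety parameters.** Besides protocol-defined AEs, section 8.2.1 names "all-cause revision and/or removal of any component of the Triathlon Total Knee with the Triathlon PSR Insert".
- **Safety analysis.** Section 8.2.2 states "The frequency and percentage of all protocol-defined adverse events will be tabulated" and then "All protocol-defined adverse events will be tabulated, and a 95% CI will be presented"; the interval method is not given. Section 11.3 says "The safety analysis will include tabulation of AE rates as well as revision/removal rates". No person-time, cumulative-incidence or other censoring-adjusted method is named for either.
- **Time-to-event analysis.** Section 8.1.2 covers the insert: "The Kaplan-Meier survival curve of all-cause revision and removal of the Triathlon PSR insert will be displayed", with a 95% CI at 10 years. Under section 4.3, exchange of the insert is a failure and ends participation. Revision of any other component is neither a failure nor a termination.
- **Denominator.** Section 8.4.4 limits the safety population to non-censored subjects who received the device. The term is not defined.
- **External comparison.** Section 6.1 says the operative-site events and the 90-day SAEs "will be collected and compared to published data", and expects AE rates comparable to those of historical PS constructs.
- **Loss.** Section 8.4.2, which sizes the 2-year endpoint, states: "After factoring in a 20% lost to follow-up rate, a total of 250 cases will be needed". No 10-year loss figure is given.

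**The concern.** A percentage is a sound summary when every subject is observed for the same time. That is nearly so for SAEs to 90 days. It is not so for operative-site AEs or for femoral, baseplate or patellar revisions over 10 years, because loss, withdrawal, death and insert exchange all shorten follow-up. A subject lost at year 1 and one followed to year 10 would carry equal weight, and the result would mix the event risk with the retention pattern.

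The plan recognises this for the insert by using Kaplan-Meier. The same attrition affects the other long-term safety outcomes, and several risks listed in section 11.2 (late loosening, wear, osteolysis) can arise late. At stake is the safety statement in section 6.1: a crude percentage set beside published rates can look comparable or different partly because follow-up differs.

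**Working it through.** **1. The plan's own figure.** The only computed figure is the primary sample size. With one-sided alpha 0.05, power 95%, SD 10.7 and margin 2.5, n = (1.645 + 1.645)² × 10.7² / 2.5² = 198.2, so 199 by the normal approximation. The exact t calculation gives 200 (power 0.950). Then 200 / (1 − 0.20) = 250. This reproduces. It shows that the 20% is an allowance for the 2-year endpoint; it says nothing about years 3 to 10.

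**2. Inputs for the illustration.** From the documents: 250 cases, 10 years, 20% loss. Assumed, because the documents give no values: a true 10-year risk F = 10%, constant event hazard, and loss independent of events.

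Event hazard: λ = −ln(0.90)/10 = 0.01054 per year.

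**3. Lost subjects kept in the denominator.** With constant loss hazard c, the crude proportion is λ/(λ+c) × [1 − exp(−10(λ+c))].

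- *20% lost in total by year 10.* c = −ln(0.80)/10 = 0.02231. Crude = 0.01054/0.03285 × (1 − 0.90 × 0.80) = 0.3207 × 0.28 = 0.0898, or **9.0%** (22.5 subjects with an event out of 250, against 25 with complete follow-up).
- *20% lost by year 2, none later.* c = −ln(0.80)/2 = 0.11157 for two years. Years 0–2: 0.01054/0.12211 × (1 − 0.7833) = 0.0187. Years 2–10: 0.7833 × [1 − exp(−8λ)] = 0.7833 × 0.0808 = 0.0633. Sum = 0.0820, or **8.2%** (20.5 subjects).

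The ratios of crude to true, 0.90 and 0.82, are almost the same for true risks of 5% and 20%.

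**4. Dependence on when events occur.** Under independent loss, the ratio of crude to true equals the average proportion still in follow-up at the event times. With 20% total loss by year 10 it therefore lies between 1.00 (all events at surgery) and 0.80 (all events just before year 10), whatever the hazard shape. Early-clustering AEs are little affected; late ones more so.

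**5. Continued loss, as an extrapolation only.** If 20% per 2 years went on, retention at year 10 would be 0.80⁵ = 0.328 and the crude figure 0.0863 × (1 − 0.90 × 0.328) = 6.1%. A simulation of one million subjects under this pattern gave 6.1% crude and 10.0% by Kaplan-Meier, so the time-to-event estimate recovers the true risk.

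**6. Non-censored read as excluding subjects lost before an event.** The denominator becomes those with an event plus those event-free at year 10:

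- 20% by year 10: 0.0898 / (0.0898 + 0.80 × 0.90) = 11.1%.
- 20% by year 2, none later: 0.0820 / (0.0820 + 0.72) = 10.2%.
- Continued loss: 0.0608 / (0.0608 + 0.328 × 0.90) = 17.1%.

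If every lost subject is dropped, whether or not an event came first, independent loss leaves the percentage at 10%.

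**The case against.** The strongest reply has five parts.

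1. *Direction.* A reader might infer that attrition always makes the PSR construct look safer. The documents do not support that. It requires lost subjects to stay in the denominator, and the undefined wording in section 8.4.4 allows a reading under which the percentage is unbiased or too high. Keeping them is the more natural reading, because availability at 2 years is a condition of the per-protocol population only. This part stands against any fixed direction, but not against the point that the denominator is unclear.
2. *Scope.* A reader might infer that no component revision gets a time-to-event analysis. Insert revision or removal does, and so does any revision in which the insert is exchanged. The gap is revisions that leave the insert in place; the documents do not say how many to expect. This stands.
3. *Size.* A reader might carry the 20% allowance forward every two years and arrive at 67% lost. Nothing in the plan expects this, and sections 4.3 and 13.3 describe retention efforts. This stands; the 6.1% and 17.1% figures are extrapolations.
4. *Comparison.* Section 6.1 sets no test, margin or decision rule, and the published rates may themselves be crude, in which case time-to-event estimates alone would create a mismatch. This stands and shapes the fix.
5. *By-visit tables.* The synopsis lists device-related AEs and UADEs as additional data, which section 8.4.1 summarises by visit. That may soften the problem for those events, but does not clearly cover all operative-site AEs, and a by-visit percentage is still not a cumulative risk.

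**Conclusion.** The point holds for operative-site AEs after the early postoperative period and for revisions that leave the insert in place. For these the plan offers only crude percentages or tabulations, and such figures do not estimate 10-year risk when follow-up is unequal.

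The direction depends on a denominator that the plan leaves undefined: most likely too low, possibly too high. For a true risk of 10%, the two loss patterns closest to the plan's own allowance give 9.0% and 8.2%, a relative understatement of about 10% and 18%. These rest on an assumed event rate, constant hazards, independent loss and all implanted cases in the denominator. The distortion shrinks if events cluster early and grows if loss continues.

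The primary SF-36 analysis, the insert survivorship analysis and the 90-day SAE counts are not called into question by this. The affected outputs are descriptive, but they feed the safety comparison in section 6.1.

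**What to change.** - **Section 8.4.4.** Define the safety population as all implanted cases and remove the term non-censored from it.
- **Section 8.2.2.** Keep simple counts and percentages for SAEs to 90 days. For first operative-site AE, and for all-cause revision or removal of any component, report cumulative incidence at 2, 5 and 10 years with 95% CIs and numbers at risk. Censor at last contact. For lost subjects this is not the termination date in section 4.3, which is the day the sponsor approves termination. Treat death as a competing event. For AEs, treat insert exchange that ends follow-up in the same way, unless it is itself counted as the event.
- **Section 11.3.** Refer to these estimates in place of an unspecified tabulation.
- **Section 6.1.** Compare with the PS construct at matched time points and for matched AE categories. Where a published source gives only crude percentages, show the crude PSR percentage beside the cumulative incidence.

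The cost is SAP wording and a few additional time-to-event runs, using event and follow-up dates that the study already collects. The long-term rates may look slightly less favourable than the crude ones.

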8.3 Missing Data

No missing data will be imputed.

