4.3 Early Withdrawal of Subjects

When and How to Withdraw Subjects

In the event that the subject is discontinued by the investigative center prior to the final study evaluation, the subject will be notified by the center that he/she is no longer in the study and a Study Termination eCRF will be completed.

The following is a list of reasons for which subjects may be withdrawn and the date of termination that should be used on the Study Termination eCRF in each situation. This list is not all inclusive:

Termination Reason Date of Termination

Death Date of death

Investigative center termination Date of study close-out visit

Lost to follow-up Date Stryker termination approval given

Voluntary withdrawal Date subject notified center of withdrawal

Revision/removal of study device Date of revision/removal procedure

Study device not implanted Date of surgery

Surgery not performed Date Stryker termination approval given

At the time of study surgery, it is required that the following components are implanted to be included in the analysis:

Triathlon PSR Tibial Insert

Compatible Triathlon Tibial Baseplate

Compatible Triathlon PS Femoral Component

o Compatible Patellar Component

All components must be cemented with respect to the bone.

Exchange of the Triathlon PSR Tibial Insert for any reason constitutes a failure and study termination for the subject.

If revision of any other component occurs during the study, the event does not constitute a failure or study termination.

If the subject fails to return for his/her follow-up appointments, every effort should be made to contact the subject to assess his/her health status. If, after attempting to contact the subject through three documented phone calls and a certified letter, the subject still does not respond, he/she will be considered lost to follow-up. A Study Termination eCRF will be completed only after notifying Stryker of the subject's status and being given approval to terminate.

In the event a subject does not have surgery, Stryker should be contacted to discuss if/when the surgery will be rescheduled. Preoperative data must be current within 4 months of the study surgery and will need to be re-collected if the surgery is rescheduled more than 4 months from the initial data collection. If the surgery is not to be rescheduled or if the subject is no longer

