8.4.4 Analysis Population

Per Protocol Population:

The study population for analysis will include all non-censored subjects who received a cemented Triathlon Total Knee with the Triathlon PSR insert and are available for primary objective evaluation at the 2-year primary endpoint.

The primary and secondary objective analyses will be based on the per protocol population.

Safety Population:

The safety population will include all non-censored subjects who received a cemented Triathlon Total Knee with the Triathlon PSR insert.

9 Study Monitoring, Auditing, and Inspecting

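### The 2-year PCS conclusion rests on completers alone with no prespecified check on missing scores, and insert survivorship is assigned to the same 2-year set

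*Combined protocol and SAP*

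**What the plan says.** Section 8.1.1 tests the mean 2-year PCS with a one-sample two-sided 90% confidence interval. Non-inferiority holds if the lower bound exceeds 44.8, which is 47.3 minus the 2.5-point margin. On the benchmark it says: "The reference value of 47.3 was derived from Triathlon PS study where subjects received a cemented Triathlon PS Total Knee with the PS Insert".

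The missing-data section (8.3) is one sentence: "No missing data will be imputed". Section 8.4.4 confines the analysis set to non-censored recipients of the cemented construct who "are available for primary objective evaluation at the 2-year primary endpoint", and adds: "The primary and secondary objective analyses will be based on the per protocol population". The only other population begins: "The safety population will include all non-censored subjects". The term non-censored is not defined.

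The expected loss appears in Section 8.4.2 only: "After factoring in a 20% lost to follow-up rate, a total of 250 cases will be needed". Section 4.3 states: "Exchange of the Triathlon PSR Tibial Insert for any reason constitutes a failure and study termination for the subject". Section 8.1.2 states: "The Kaplan-Meier survival curve of all-cause revision and removal of the Triathlon PSR insert will be displayed".

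The plan does work to limit loss. Section 4.3 requires three phone attempts and a certified letter, with sponsor approval, before a subject is terminated as lost. Section 7.6 lists an unavailable primary endpoint as a possible major deviation, and Section 13.3 allows visit reimbursement and stipends. Section 7.4 requires missing data to be explained, and the termination form in Section 4.3 records reason and date. The Evaluation Schedule collects SF-36 preoperatively, at 6 weeks, at 1 year and at 2 years.

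**The concern.** Raising enrolment from 200 to 250 protects power. It does nothing about who is missing. If subjects without a 2-year score do worse than those with one, the completer mean overstates the mean among all implanted subjects and non-inferiority is easier to declare for that wider group. Part of the loss is tied to outcome by rule: an insert exchanged before 2 years takes a device failure out of the PCS mean. Earlier SF-36 scores and recorded reasons for missingness will exist, but no analysis uses them to test the 2-year result.

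The second issue is the survivorship set. An exchange before 2 years ends participation, so that subject is not available at 2 years. If the per protocol set governs the Kaplan-Meier analysis, as Section 8.4.4 says of all secondary objectives, these events cannot enter the curve. Deaths and losses before 2 years drop out with them.

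**Working it through.** **Inputs.** Reference 47.3, SD 10.7, margin 2.5, 5% significance, 95% power, 200 evaluable, 20% loss, 250 enrolled (Section 8.4.2); success bound 44.8 and 90% interval (Section 8.1.1). The PCS gap between missing subjects and completers, *d*, and the realised missing fraction, *f*, are assumptions. The documents give only the 20% planning allowance.

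**The plan's own figure.** n = (SD × (1.645 + 1.645) / margin)² = (10.7 × 3.29 / 2.5)² ≈ 198.3, rounded up to 199. By noncentral t, power is 94.95% at 199 and 95.03% at 200, so 200 is right. 200 / (1 − 0.20) = 250. The sample size stands.

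**Passing threshold.** SE at n = 200 is 10.7/√200 = 0.757. The lowest passing mean is 44.8 + 1.645 × 0.757 = 46.04 (46.05 with t).

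**Bias for an all-implanted target.** The all-implanted mean equals the completer mean minus *f·d*, so the bias is b = *f·d*. If the all-implanted mean were exactly 44.8 and the reference is taken as fixed, the chance of declaring non-inferiority is 1 − Φ(1.645 − b/SE). For 10% missing, n = 225 and SE = 10.7/√225 = 0.713.

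| Missing | Assumed *d* | Bias | Chance of declaring |
|---|---|---|---|
| any | 0 | 0 | 5% |
| 20% | 2.5 | 0.50 | 16% |
| 20% | 5 | 1.00 | 37% |
| 10% | 2.5 | 0.25 | 10% |
| 10% | 5 | 0.50 | 17% |

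If the missing 20% did 2.5 points better, the chance would fall to about 1%.

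**Gap needed to overturn a positive result.** The lower bound reaches 44.8 when *d* = (observed mean − 1.645 × SE − 44.8) / *f*, with SE held at its complete-case value.

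| Observed mean | 20% missing | 10% missing |
|---|---|---|
| 46.5 | 2.3 | 5.3 |
| 47.0 | 4.8 | – |
| 47.3 | 6.3 | 13.3 |
| 48.0 | 9.8 | – |

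For example, (47.3 − 1.245 − 44.8) / 0.2 = 6.3. Adding the binomial variance of the missing fraction lowers the 20% column only to 2.26, 4.70, 6.15 and 9.47.

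**Offset from the reference.** If 47.3 is itself a completers-only mean, the net bias is *f·d* − *f_ref·d_ref*. With 20% and 5 points in this study, a reference with 10% and 5 points leaves 1.0 − 0.5 = 0.5 (about 16%). A reference with 20% and 5 points leaves 0 (5%).

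**Survivorship.** No gap has to be assumed here. Section 8.1.2 defines the event as revision or removal of the insert, Section 4.3 terminates the subject at that event, and Section 8.4.4 requires 2-year availability for secondary objectives. Taken together, the curve can show no insert exchange before the 2-year visit. It describes survival among those who reached that visit, not survival from surgery.

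**The case against.** The strongest reply is that the stated test is not wrong. Declining to impute is acceptable for a primary analysis in a single-arm post-market study, and the interval has its nominal 5% error for the population it names. That stands.

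A reader might infer from the first table that the trial's false-positive rate is 16% or 37%. The documents do not support this. Those figures need a different target (all implanted subjects), a true mean exactly at the boundary, the full planning allowance realised as loss, and a gap that no section supplies. They are illustrations only.

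The effect may also be nil. The documents do not say how missing data were handled for 47.3, and similar selection there would cancel the bias. At the planned mean the gap needed is about 2.5 times the margin (6.3/2.5). If the completer mean is truly 47.3, the observed mean falls between 46.05 and 46.5 in only about 10% of trials. All of this limits the consequence. It does not supply the missing check, and an unknown reference handling means that a reader cannot tell whether the bias cancels.

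A reader might also infer that device failures vanish from the study, or that exchanged subjects are excluded from safety. Neither is established. Sections 8.2.1 and 11.3 include revisions and removals in the safety summaries. Section 4.3 lists components that must be implanted for inclusion in the analysis, which suggests a meaning of non-censored that keeps exchanged subjects in. The term simply needs a definition.

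Finally, the synopsis mentions change in SF-36, and Section 8.4.1 provides by-visit summaries of additional data. Neither deals with absent 2-year scores.

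**Conclusion.** The omission is certain: the sole inference on 2-year PCS is a complete-case mean, and the anticipated 20% loss is met in the analysis only by a larger N. The practical effect is conditional. The result carries over to all implanted subjects only if missingness is unrelated to 2-year PCS. The effect is small near the planned mean of 47.3 and could decide the result just above the 46.05 threshold. Its direction is unknown. Neither the sample size nor the primary test is in error.

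The survivorship conflict is separate and is the firmer textual point: as written, Section 8.4.4 undercuts the 10-year endpoint in Section 8.1.2. Both matters should be corrected before the 2-year data are analysed, because checks chosen after the result is known carry less weight.

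**What to change.** Keep the complete-case test as primary. In Section 8.3, restrict the no-imputation rule to the primary analysis, and prespecify two supportive analyses in implanted subjects alive at 2 years (with a stated rule for unknown vital status):

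- (a) A likelihood-based repeated-measures model of preoperative, 6-week, 1-year and 2-year PCS, giving the 2-year mean and 90% interval. Label it a missing-at-random estimate that projects the unobserved scores of exchanged subjects.
- (b) A delta-adjusted tipping-point analysis reporting the gap at which the lower bound reaches 44.8, with exchanged subjects given a stated unfavourable value. Label it a composite target, different from (a).

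Report deaths separately. Tabulate reasons for missingness, and the baseline and 1-year PCS of completers and non-completers. State whether 47.3 is a completers-only mean and with what loss. If it is, or if this is unknown, read (a) and (b) as robustness checks and not as replacement tests, since the penalty would fall on one side only.

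In Section 8.4.4, run the Kaplan-Meier analysis in all implanted subjects from surgery. Define non-censored so that insert exchange does not remove a subject from the survivorship or safety analyses.

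The cost is SAP wording and modest programming, with no extra subjects or visits. The conclusion may become more qualified.
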